### **3.3 Inclusion and Exclusion Criteria and Sample Size Estimation**

(1) Patient Selection: Meeting the diagnostic criteria for NPC; patients who have not yet received concurrent chemoradiotherapy; meeting the case inclusion and exclusion criteria; patients voluntarily joining this clinical trial and signing the informed consent form.

(2) Sample Size Estimation: The Delphi method is used to determine the non-inferiority margin of the observation endpoint. After consulting senior oncology practitioners, we defined an 8% reduction in the incidence of RIOM as a clinically acceptable non-margin of error. Under the conditions of test level  $\alpha=0.05$  and test efficacy  $1-\beta=0.9$ , the proportion of cases in the two groups is 1:1. Using the module of non-destructiveness Tests for Two Proportions in PASS 15.0 statistical analysis software, we determined that a sample size of 81 was required per group. Considering a 10% loss to follow-up rate, we estimated that 90 cases would be required in each group, for a total of 180 cases.

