Among radiation-induced adverse reactions, radiation-induced oral mucositis (RIOM) occurs in over 80% of patients undergoing radiotherapy. More than 50% of these patients even develop Grade 3-4 RIOM. Current clinical strategies for the prevention and treatment of RIOM include oral care, gargling medications, nebulized inhalation drugs, and local application of epidermal growth factor. Nebulized drug therapy has become an important method in cancer supportive care due to its ability to increase local drug concentration, decrease blood drug concentration, and achieve better compliance. MASCC/ISOO, ESMO, and other authoritative guidelines agree that there is currently no specific drug for the prevention and treatment of RIOM. Treatment focuses primarily on symptom relief and reducing complications. Epidermal Growth Factor (EGF) and corticosteroids are recommended. However, the long-term use of corticosteroids increases the risk of fungal infection and tends to cause radiotherapy interruptions. There is an urgent need for a highly effective and low-toxicity drug to prevent and treat RIOM. Zhao Weiwei and Chai Xieli, among others, concluded from relevant domestic and international studies that nebulized

inhalation therapy is a non-invasive, highly efficient, and low-side-effect approach in oncology treatment. However, the application of nebulized Sapylin is currently only reported in lung cancer, and its nebulized use in CCRT for NPC is rarely reported. Therefore, nebulized drug therapy for RIOM is one of the current research trends. Nishii et al. found that local application of corticosteroids can relieve edema, inhibit inflammation, and alleviate patient symptoms. Systemic use of corticosteroids tends to reduce radiotherapy interruptions but does not decrease the incidence or severity of RIOM. However, long-term local use of corticosteroids increases the risk of oral fungal infections. Nebulized traditional Chinese medicines lack multi-center clinical trials to evaluate their efficacy, thus limiting their application in NPC patients. However, a safer and more effective strategy is currently unavailable. Therefore, finding a drug with high efficacy and low side effects to improve RIOM in NPC patients and, consequently, enhance CCRT efficacy is crucial.

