### (2) Statistical Analysis

① General Principles: One-sided tests will be used for superiority tests, while two-sided tests will be used for other statistical tests. Quantitative indicators will be described using the number of cases, mean, standard deviation, median, minimum, and maximum. Categorical indicators will be described using the number of cases and percentages. All statistical analyses will be conducted using SPSS 26.0 statistical software.

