## VIII. Preliminary Research Foundation and Working Conditions

The research team conducted a retrospective study on 32 NPC (NPC) patients from 2016 to 2019. The study observed the effect of nebulized Sapylin and Dexamethasone on the incidence rate of RIOM (radiation-induced oral mucositis) and the efficacy of CCRT (Concurrent

Chemoradiotherapy) during concurrent chemoradiotherapy. Results showed: The CCRT combined with nebulized Sapylin group had a lower incidence rate of RIOM and Grade III-IV RIOM compared to the CCRT combined with nebulized Dexamethasone group (43.75% vs 68.75%) and (12.5% vs ≥31.3%), respectively. Furthermore, the CCRT combined with nebulized Sapylin group was superior to the CCRT combined with nebulized Dexamethasone group in terms of objective response rate (ORR) (87.5% vs 62.5%), median overall survival (OS) (53.7M vs 46.4M), and median progression-free survival (PFS) (27M vs 23M). Moreover, comparison of the efficacy and survival analysis between the CCRT combined with nebulized Sapylin group and the CCRT combined with nebulized Dexamethasone group revealed that the nebulized Sapylin inhalation group showed a trend toward reducing the incidence rate of Grade III-IV RIOM and enhancing CCRT efficacy in NPC patients, with no obvious toxic side effects observed. Therefore, this project will conduct a non-inferiority, parallel-design, randomized controlled study of nebulized Sapylin versus nebulized Dexamethasone for the prevention and treatment of radiation-induced oral mucositis in NPC.

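### The 81 per group does not follow from the 8% non-inferiority margin at the RIOM incidences the protocol gives, so the stated 90% power rests on undisclosed assumptions

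*Protocol*

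**What the plan says.** Protocol II.3.3(2) sets the margin by a Delphi exercise among senior oncology practitioners: "we defined an 8% reduction in the incidence of RIOM as a clinically acceptable non-margin of error". It then gives alpha 0.05, power 0.9 and 1:1 allocation, names the software ("Using the module of non-destructiveness Tests for Two Proportions in PASS 15.0 statistical analysis software", evidently the non-inferiority module), and concludes: "we determined that a sample size of 81 was required per group". Allowing for 10% loss, this becomes 90 per group and 180 in total. Section III.5(2) repeats the paragraph.

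Neither place states the assumed RIOM incidence in either arm, the assumed true difference, the test statistic, the sidedness of alpha, or whether the 8% is absolute or relative.

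Three other sections bear on the calculation:

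- II.7(2), General Principles, on sidedness: "One-sided tests will be used for superiority tests, while two-sided tests will be used for other statistical tests".
- VIII, the retrospective pilot of 16 patients per arm. Any-grade RIOM was lower with Sapylin than in the "nebulized Dexamethasone group (43.75% vs 68.75"%); grade III-IV was 12.5% versus 31.3%.
- I.1 Background: "radiation-induced oral mucositis (RIOM) occurs in over 80% of patients undergoing radiotherapy".

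None of these rates is linked to the sample size.

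**The concern.** A non-inferiority sample size for two proportions depends on the margin, the control rate and the assumed true difference. The protocol presents the calculation as complete but reports only the margin. When the missing inputs are filled from the protocol's own incidences, the answer is either several times larger than 81 or about half of it.

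The primary conclusion depends on this. A reader takes 90% as the probability that the trial shows non-inferiority if Sapylin is about as good as dexamethasone. If the figure holds only when Sapylin is substantially better, a trial of two truly similar drugs would probably end inconclusive with 180 patients, and nothing in the protocol would have warned of it. The only arm-specific rates available are 16 versus 16 retrospective patients.

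The wording adds to the difficulty. RIOM is an adverse outcome, so a tolerated loss would be an increase in incidence, yet the margin is described as a reduction.

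**Working it through.** **Inputs.** Margin m = 0.08 (II.3.3(2), first read as percentage points); power 0.90; 1:1 allocation. The sample-size paragraph does not give the sidedness of alpha, so both one-sided 0.05 and one-sided 0.025 are shown. The rule in II.7(2) makes a non-inferiority test two-sided, which implies 0.025. RIOM rates: pilot 68.75% (dexamethasone) and 43.75% (Sapylin) from VIII; 80% from I.1.

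**Formula (per group, unpooled normal).** With pc the control rate and pe the Sapylin rate,

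n = (z_α + z_0.90)² × [pc(1−pc) + pe(1−pe)] / [m − (pe − pc)]²

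where (z_α + z_0.90)² = 8.564 at 0.05 and 10.507 at 0.025.

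Worked example, both arms 68.75%: 8.564 × 0.4297 / 0.0064 = 575.0, and 10.507 × 0.4297 / 0.0064 = 705.5.

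| Assumed RIOM, control / Sapylin | n at 0.05 | n at 0.025 |
|---|---|---|
| 68.75% / 68.75% | 575 | 706 |
| 80% / 80% | 429 | 526 |
| 80% / 68.75% | 87 | 107 |
| 68.75% / 43.75% (pilot) | 37 | 45 |

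The Farrington-Manning variance hardly changes the main rows: 575 / 705, 431 / 530 and 38 / 47 for the first, second and fourth.

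**Other readings of the 8%.**

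- Relative margin at 68.75% (0.08 × 0.6875 = 0.055): 1217 / 1493 at equal rates, 43 / 53 at the pilot rates.
- Literally a required reduction of 8 points, at the pilot rates: 137 / 168.

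**Attempt to reproduce 81.** Solving the formula for n = 81 with an 8-point margin gives:

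| Control rate | Sapylin rate needed at 0.05 / 0.025 | Implied true benefit (points) |
|---|---|---|
| 68.75% | 54.6% / 52.2% | 14.1 / 16.5 |
| 80% | 68.0% / 65.6% | 12.0 / 14.4 |
| 90% | 82.2% / 80.0% | 7.8 / 10.0 |
| Equal rates | 96.9% / 97.5% in both arms | 0 |

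The protocol states none of these pairs.

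Two superiority calculations, with no margin and pooled variance, also reach 81:

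- Any-grade pilot rates, two-sided 0.05: 80.65, so 81. Under the one-sided superiority rule in II.7(2), the same rates give 66.
- Grade III-IV pilot rates as printed (31.3% versus 12.5%), one-sided 0.05: 80.996, so 81.

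These are possible origins, not evidence of what was done.

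**Power with 81 evaluable per group**, 8-point margin: Φ{[0.08 − (pe − pc)] / √([pc(1−pc) + pe(1−pe)]/81) − z_α}.

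| True Sapylin benefit (points) | Control 68.75%: 0.05 / 0.025 | Control 80%: 0.05 / 0.025 |
|---|---|---|
| 0 | 29% / 19% | 35% / 25% |
| 5 | 54% / 42% | 63% / 51% |
| 10 | 77% / 67% | 85% / 76% |
| 15 | 92% / 86% | 95% / 91% |
| 25 (pilot) | above 99% / 99% | above 99% / above 99% |

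**Strength of the pilot.** The difference is −25 points with standard error √[(0.6875×0.3125 + 0.4375×0.5625)/16] = 0.170, so the 95% CI is about −58 to +8 points.

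**Dropout step.** 81 / 0.9 = 90, which is correct.

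**The case against.** The strongest reply is that no arithmetic error has been shown. PASS needs a control rate and a true difference, neither is reported, and ordinary inputs such as 80% versus 68% at one-sided 0.05 do give 81. The background rate of over 80% is also open-ended: equal rates near 97%, or 80.6% versus 68.75% at one-sided 0.05, fall within it and give 81. A non-inferiority trial may legitimately be powered on an expected benefit, and II.3.3(2) may simply have left that unsaid. The reduction wording could be a translation slip.

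Part of this stands. It cannot be shown that the software was misused, and the trial should not be called underpowered without qualification, because under the full pilot benefit 81 exceeds the 37 to 45 needed. Powering on a benefit is acceptable if declared.

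It does not rescue the paragraph. The protocol states neither 97% nor 80.6%, and the 80.6% pairing would use the pilot's dexamethasone rate as the Sapylin rate. The stated inputs do not determine 81, and the protocol's own incidences do not supply what is missing. Nor does the 90% describe either natural scenario, equal efficacy or the pilot effect.

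A further objection is that fixing the total at 180 prejudges the answer before the inputs are known. That is a fair caution: the retrieved inputs may show that the margin never entered the calculation. The paragraph would then have to say so and rest 180 on the power table.

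**Conclusion.** The point holds. As written, an unconditional 90% power is claimed that the stated design does not deliver. At the protocol's incidences the required number runs from 37 / 45 per group (full pilot benefit) to 575 / 706 (no difference at 68.75%), at one-sided 0.05 / 0.025. At 81 evaluable per group, power runs from 19–35% with no true difference at 68.75–80% to about 99% at the pilot difference.

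These figures assume an absolute 8-point margin on any-grade RIOM incidence, a normal-approximation test, and 81 evaluable patients per arm. A relative margin also fails to give 81 at the 68.75% control rate, whether the arms are equal or follow the pilot. Because the claim underlies the primary non-inferiority conclusion, it must be corrected.

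**What to change.** In both II.3.3(2) and III.5(2):

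1. Retrieve the PASS inputs actually used. State the assumed RIOM incidence in each arm with its source, the test statistic, and the sidedness of alpha, consistent with II.7(2).
2. State the scale and direction of the margin. If it is what the Delphi panel meant, for example: non-inferiority is concluded if the upper confidence limit for the Sapylin minus dexamethasone RIOM incidence lies below +8 percentage points.
3. Replace the unconditional 90% with the power of 81 per group over a range of true differences, including none, as tabulated above. If a true benefit of Sapylin was assumed, say so and give its size.

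Non-inferiority stays the primary hypothesis and the total stays at 180. The cost is finding the PASS output and rewording two paragraphs, plus a stated power that is conditional and less favourable than the present one.

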### **3.4 Randomization Method**

This study employs a block randomization method. Random sequences are generated by independent statistical personnel who are not involved in clinical procedures, utilizing statistical software. After patient enrollment, the research personnel access a centralized remote randomization system to obtain the patient's treatment assignment result, thereby allocating patients to either the Sapylin group or the Dexamethasone group at a 1:1 ratio. This procedure ensures the separation of random sequence generation and execution, maximizing the randomness and concealment of the allocation.

### **3.5 Clinical Treatment Protocol**

#### (1) Experimental Group

Concurrent Radiotherapy Dose: Nasopharyngeal primary tumor site (PTVnx): 69.96Gy/2.12Gy/33F; High-risk planning target volume (PTV1): 60.06Gy/1.82Gy/33F; Low-risk

planning target volume (PTV2): 54.12Gy/1.64Gy/33F; Cervical lymph nodes (PTVnd): 66~69.96Gy/2~2.12Gy/33F; 5 times per week, for a total of 6-7 weeks.

Concurrent Chemotherapy: Cisplatin (80-100 mg/m^2, Q3W, 3 times during CCRT); Sapylin: 1 KE/time, nebulized, QD, starting from Day 1 of CCRT until the end of radiotherapy.

(2) Control Group:

Concurrent Radiotherapy Dose: Nasopharyngeal primary tumor site (PTVnx): 69.96Gy/2.12Gy/33F; High-risk planning target volume (PTV1): 60.06Gy/1.82Gy/33F; Low-risk planning target volume (PTV2): 54.12Gy/1.64Gy/33F; Cervical lymph nodes (PTVnd): 66~69.96Gy/2~2.12Gy/33F; 5 times per week, for a total of 6-7 weeks.

Concurrent Chemotherapy: Cisplatin (80-100mg/m^2, Q3W, 3 times during CCRT); Dexamethasone: 10mg/time, nebulized, QD, starting from Day 1 of treatment until the end of radiotherapy.

### 3.6 Patient Follow-up

(1) Observation and follow-up personnel will conduct patient follow-up via outpatient visits, telephone tracking, home visits, etc., to observe and evaluate the patient's RIOM grading, adverse effects, and weight changes

(2) Follow-up time requirements: The follow-up duration is set at 3 months, with assessments once a month.

## 4. Research Design

Study Period	Key Responsibilities
Jul 2022 - Jun 2024	1. Initiate recruitment; 2. Screen eligible NPC cases, determine baseline data and collect indicators, perform randomization, and complete the enrollment of the expected sample size; it is planned to recruit 90 patients in the 2 years (45 in the experimental group, 45 in the control group) and conduct follow-up observations on these subjects; 3. Follow up each enrolled case for 1 year; 4. The enrolled cases will proceed according to the trial steps designed for each group, including patient follow-up, disease assessment, and indicator collection and follow-up.
Jul 2024 - Jun 2026	1. Screen eligible NPC cases, determine baseline data and collect indicators, perform randomization, and complete the enrollment of the expected sample size; it is planned to recruit 90 patients in the second 2 years period (45 in the experimental group, 45 in the control group); 2. Follow up each enrolled case for 1 year, and perform data registration and statistics; 3. The enrolled cases will proceed according to the trial steps designed for each group, including patient follow-up, disease assessment, and indicator collection and follow-up.

Jul 2026 - Jul 2027	1. Statistical analysis, thesis writing, domestic and international exchange, and promotion application.
---------------------	----------------------------------------------------------------------------------------------------------

## 5. Study Subjects

Observe the data of NPC patients with complete clinical and pathological data who underwent concurrent chemoradiotherapy at the Head and Neck Tumor Ward of the Cancer Hospital of the Affiliated Hospital of Guangdong Medical University between July 2022 and July 2026.

## 6. Evaluation Indicators

- (1) Primary Evaluation Indicator: Incidence and severity of RIOM.
- (2) Secondary Evaluation Indicators: ①Duration of RIOM; ②Rate of completion of treatment measures; ③Adverse events classified according to CTCAE 5.0; ④Changes in BMI.

**Adverse Event (AE)** Any untoward medical occurrence in a subject during the clinical trial, which does not necessarily have a causal relationship with the treatment. An adverse event can be any unfavorable and unintended sign (including abnormal laboratory findings), symptom, or temporary illness associated with the use of the drug, whether or not related to the drug.

**Serious Adverse Event (SAE)** All serious adverse events occurring during the clinical trial must be recorded in the Serious Adverse Event (SAE) report. The occurrence of any of the following conditions should be considered a serious adverse event:

- ① Results in death;
- ② Is life-threatening;
- ③ Requires inpatient hospitalization or prolongation of existing hospitalization;
- ④ Results in persistent or significant disability/incapacity;
- ⑤ Results in a congenital anomaly or birth defect;
- ⑥ Other.

**Causality Assessment of Adverse Events** While recording in detail any abnormal symptoms, signs, laboratory tests, or other special examinations occurring during the clinical study, a causality assessment should be performed. According to the criteria for adverse reaction/event analysis, the causality assessment is classified as: 1-Definitely related; 2-Probably related; 3-Possibly related; 4-Probably unrelated; 5-Definitely unrelated.

- ① Is there a reasonable temporal relationship between the start of medication and the appearance of the suspected adverse reaction?
- ② Does the suspected adverse reaction fit the known adverse reaction profile of the drug? ③ Can the suspected adverse reaction be explained by the effects of concomitant medications, the patient's clinical condition, or other therapies?
- ④ Does the suspected adverse reaction disappear or alleviate after stopping or reducing the drug?
- ⑤ Does the same reaction reappear after re-exposure to the suspected drug?

Causality Determination Criteria: Determined sequentially according to the above indicators 1-5.

Causality Determination Table for Adverse Reactions					
Judgment Result	Assessment Indicators				
	①	②	③	④	⑤
Definitely Related	+	+	-	+	+

Probably Related	+	+	-	+	?
Possibly Related	+	+	+	±	?
Probably Unrelated	+	-	±	±	?
Definitely Unrelated	-	-	+	-	-

Remarks: "+" indicates affirmation/positive; "-" indicates negation/negative; "±" indicates difficult to affirm or deny; "?" indicates unknown/unclear.

The relationship between adverse events (including serious adverse events) and the drug should be determined whenever possible. If the assessment determines the relationship to be definitely related, probably related, or possibly related, the event will be considered an adverse reaction caused by the drug, and its severity will be used to determine if it should be classified as a serious adverse event.

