Previously, through extensive literature review, we found that while Sapylin administered via traditional methods can reduce malignant pleural effusion and improve immunity in cancer patients, patients experience reactions such as injection site pain and fever. In contrast, the nebulized inhalation method is not only safe and effective but also improves the patient's immunity, inhibits tumor cell proliferation, and enhances the efficacy of tumor chemotherapy drugs. Furthermore, we have currently collected 32 clinical cases (16 cases in the CCRT + Sapylin group, 16 cases in the CCRT + Dexamethasone group). The results revealed that nebulized Sapylin inhalation can improve the efficacy of CCRT and prolong patient survival, improve the incidence and severity of RIOM in NPC patients, and show no obvious toxic side effects. However, the application of nebulized Sapylin in cancer treatment is currently only seen in lung cancer studies both domestically and internationally. Whether its application in NPC patients can improve the efficacy of concurrent chemoradiotherapy and what its safety profile is like are rarely reported domestically or internationally and require further research and exploration. Therefore, we intend to explore the impact of Sapylin on the efficacy of concurrent chemoradiotherapy and the incidence and severity of RIOM in NPC patients via nebulized inhalation, aiming to find a highly efficient, low-toxicity method for NPC specialists and patients that can reduce the occurrence and severity of RIOM and improve the efficacy of CCRT.

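### The causality table gives an adverse event outside the drug's known reaction profile no route to a related class

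*Protocol*

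**What the plan says.** Section II.6 (Evaluation Indicators) of the protocol asks five questions about each suspected reaction: ① timing, ② fit with what is already known of the drug, ③ another explanation, ④ improvement on stopping or reducing, ⑤ recurrence on re-exposure. The second reads "Does the suspected adverse reaction fit the known adverse reaction profile of the drug". The rule for combining them is "Causality Determination Criteria: Determined sequentially according to the above indicators 1-5", followed by a table with one row per class. The remarks under the table say that an event in the classes "Definitely related", "Probably related" or "Possibly related" is a reaction: "the event will be considered an adverse reaction caused by the drug". The same sentence then uses the severity of such an event to decide whether it is classified as serious.

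On prior knowledge, section I.2 (3) says of nebulised Sapylin in nasopharyngeal carcinoma that its effect on treatment efficacy and "what its safety profile is like are rarely reported domestically or internationally". For the comparator class, section I.1 states that "long-term local use of corticosteroids increases the risk of oral fungal infections". Sections II.1.2 and II.2.1 make the safety of nebulised Sapylin a stated aim.

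**The concern.** A causality rule for a little-studied use of a product should be able to recognise a reaction that nobody has described before. This table cannot. It makes prior knowledge of the reaction a necessary condition for relatedness, so strong individual evidence (timing, no competing cause, resolution on stopping, even recurrence on re-exposure) does not help if the event is new.

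Three things depend on the label: whether the event is reported as an adverse reaction, how the remark on serious classification applies to it, and whether the sponsor is notified when a patient drops out because of it (section III.3.3 requires that notice for events judged related to the study drug).

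**Working it through.** The plan gives no figure on this point, so there is none to reproduce. The check is of the table's logic.

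**Input: the table and its legend (section II.6).** Per the legend, + is yes, − is no, ± is hard to affirm or deny, ? is unknown.

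| Class | ① | ② | ③ | ④ | ⑤ |
|---|---|---|---|---|---|
| Definitely Related | + | + | − | + | + |
| Probably Related | + | + | − | + | ? |
| Possibly Related | + | + | + | ± | ? |
| Probably Unrelated | + | − | ± | ± | ? |
| Definitely Unrelated | − | − | + | − | − |

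**Step 1: column ②.** It reads +, +, +, −, −. A + on ② is necessary for every related class. No row accepts ± or ? under ②, so an event whose fit with the known profile is uncertain has no class at all.

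**Step 2: enumeration.** Fix ② and let each of the other four indicators take any of the four symbols: 4 × 4 × 4 × 4 = 256 patterns. Match them strictly (symbols must be identical) and loosely (a ± or ? printed in the table accepts any answer).
- ② = −: 0 of 256 reach a related class, strictly or loosely.
- ② = ± or ?: 0 of 256 reach any row, strictly or loosely.
- ② = +, strict: 3 of 256 reach a related class, namely the three printed related rows.

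**Step 3: a worked event.** Take plausible timing, not in the known profile, no other explanation, resolved on stopping, no re-exposure: + − − + ?.
- Strict reading: the *Probably Unrelated* row has ± under ③ and ④, but this event has a clear − and a clear +. It fits no row.
- Loose reading: it falls to *Probably Unrelated*.
- Change only ② to +: the pattern + + − + ? is *Probably Related*.

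With positive re-exposure as well (+ − − + +), the result is again no row (strict) or *Probably Unrelated* (loose). The same event with ② = + is *Definitely Related*.

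**Step 4: what depends on the label.**
- Sections II.3.2 (4) and II.6: all adverse events are recorded and CTCAE-graded whatever their cause, and all serious adverse events must be recorded under outcome criteria. Neither uses the table.
- Section II.6 remarks: the reaction label and the sentence on serious classification do use it. That sentence also sits awkwardly beside the outcome criteria in the same section, which make no reference to causality.
- Section III.3.3: the sponsor notice for dropouts due to a drug-related event uses the causality judgement.

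**The case against.** The best defence is that the safety endpoint does not use this table. The secondary endpoint is adverse events graded by CTCAE 5.0, recorded regardless of cause, and the Safety Analysis Set has no causality filter. An unexpected event stays in the data and loses only a label. That stands, and it limits the point.

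A reader might infer that the between-arm safety comparison is tilted towards Sapylin. The documents do not support this. No comparison of attributed reactions is planned. The rule is also the same in both arms: a new dexamethasone effect is shut out too, and a Sapylin effect already known, such as the fever described for the injected routes, can still count.

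A reader might also infer that Sapylin has practically no known profile. The protocol does not go that far. Indicator ② refers to the drug, not to the nebulised route, and names no reference document. Section I.2 (3) describes nebulised use in advanced lung cancer as well as a six-patient inhalation series, and Table 2 in section VIII grades adverse events in 16 patients given nebulised Sapylin. The profile in this setting is thin, not empty.

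Finally, the re-exposure needed for *Definitely Related*, read beside the withdrawal of patients after a serious event (section III.3.1), looks like a further defect. It has no consequence here, because the remarks treat the three related classes alike.

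None of this supplies a route from a negative answer on ② to a related class. The statement that causality is determined where possible allows an event to go unassessed; it does not allow it to be called related.

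**Conclusion.** The point holds as a defect in a stated rule. Under either reading of ±, an event outside the known profile cannot be classed as related, in either arm. It matters most for nebulised Sapylin, because the protocol itself calls its safety in this disease rarely reported and sets out to evaluate it.

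The reach is limited to the adverse-reaction label, the remark on serious classification and the sponsor notice for drug-related dropouts. The primary endpoint, sample size, primary analysis, all-causality CTCAE rates and recording of serious events are untouched. The correction should be made, but it is of moderate rather than critical weight.

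The conclusion assumes that assessors apply the table as printed. The enumeration describes the structure of the rule, not how often such events will occur; the protocol gives no basis for estimating that.

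**What to change.** Add to section II.6, at the table and its remarks, that an event with plausible timing (① +) and no other explanation (③ −) is at least *Possibly Related* whatever the answer to ②. State that this rule takes precedence over the *Probably Unrelated* row, which is then limited to events with another explanation. Say also where an event with an unclear alternative explanation (③ ±) goes, so that limiting that row does not open a new gap.

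Changing ② to ± in the *Possibly Related* row would not be enough: under the legend, ± means the answer is unclear, so a clear − would still be excluded.

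Two further sentences are needed. One should say that seriousness follows the outcome criteria in II.6 regardless of causality. The other should say that the between-arm safety comparison stays on all-causality CTCAE events.

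The cost is a protocol wording change, a matching change to any case report form page that carries the table, and re-attribution of events already assessed. Somewhat more events will be labelled possibly related.

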#### (4) Adverse Events (AEs)

All observed adverse events (AEs) will be recorded and graded daily by the clinician based on patient complaints, physical examination, and laboratory test results, according to the Common Terminology Criteria for Adverse Events (CTCAE) version 5.0 published by the National Cancer Institute (NCI).

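### The causality remarks classify related events as serious by severity, which conflicts with the protocol's own outcome-based SAE definition

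*Protocol*

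**What the plan says.** All the text at issue is in Part II, section 6 (Evaluation Indicators), apart from the grading rule in section 3.2(4).

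- **Adverse event.** An untoward occurrence counts as an adverse event even without causation: "which does not necessarily have a causal relationship with the treatment".
- **SAE definition.** A list of outcomes is introduced by "The occurrence of any of the following conditions should be considered a serious adverse event". One item is "Requires inpatient hospitalization or prolongation of existing hospitalization"; the last is an unspecified Other.
- **SAE recording.** "All serious adverse events occurring during the clinical trial must be recorded in the Serious Adverse Event (SAE) report".
- **Causality remarks, under the determination table.** They open with "The relationship between adverse events (including serious adverse events) and the drug should be determined whenever possible". The next sentence begins "If the assessment determines the relationship to be definitely related, probably related, or possibly related", says such an event counts as a reaction to the drug, and ends "its severity will be used to determine if it should be classified as a serious adverse event".
- **Severity.** Section 3.2(4) has all adverse events graded daily "according to the Common Terminology Criteria for Adverse Events (CTCAE) version 5.0".

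**The concern.** Seriousness, severity and causality are three separate attributes of an adverse event. The SAE definition keeps them apart, because an event is serious if a listed outcome occurs, whatever its grade or cause. The final causality remark ties them together: relatedness is judged first, and severity then decides SAE status. It states no severity threshold.

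The investigator therefore has two operative instructions in one section, and they can give different answers for the same event. SAE classification is a rule that site staff apply from the protocol during the trial, so a later analysis document cannot repair it. What is at stake is whether SAE forms are completed consistently and whether SAE counts in the two arms mean the same thing. Safety is a stated aim (Part II, section 2.1), and the protocol describes nebulised use of the test product in this population as rarely reported.

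**Working it through.** No arithmetic applies. The check sets the two rules side by side and applies each to the same events.

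**The rules**

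| | SAE definition | Final causality remark |
|---|---|---|
| Criterion | Any listed outcome | Severity, no threshold given |
| Causality condition | None | Judged definitely, probably or possibly related |
| Events judged unrelated | Covered | Not mentioned |

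**Internal order.** The first sentence of the remarks assesses causality for events that include SAEs, so SAE status already exists at that point. The last sentence assigns SAE status after causality. The two sentences imply opposite sequences.

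**Is severity a usable stand-in for outcome?** Only in part. In Appendix 3, grade 5 is death, grade 4 is life-threatening for the symptom items, and grade 3 mentions hospitalisation for diarrhoea and for the item on episodes per 24 hours. The blood count grades rest on laboratory cut-offs alone up to grade 4. Oral mucositis grades 1 to 3 rest on symptoms, pain, oral intake, diet and need for intervention, with no reference to hospital stay.

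**Three test cases**

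1. *Related grade 2 oral mucositis that prolongs a hospital stay.* Under the definition it is an SAE. Under the remark it need not be, since grade 2 describes moderate pain and a modified diet.
2. *Fatal or hospitalising event judged probably or definitely unrelated.* Under the definition it is an SAE. The remark gives it no classification step.
3. *Related grade 3 fall in white cells (below 2.0 to 1.0 ×10⁹/L) with no listed outcome.* Under the definition it could qualify only through the unspecified Other. Under the remark it could be called an SAE on severity.

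Cases 1 and 2 can lower the SAE count; case 3 can raise it. High-grade laboratory events of the kind in case 3 do arise. Table 2 of the retrospective series in Part VIII lists grade III anaemia in 3 of 16 Sapylin and 5 of 16 dexamethasone patients, and grade III white-cell decrease in 2 and 4 of 16. That table does not say whether any of these met a listed outcome, so it cannot be used to estimate a misclassification rate.

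**The case against.** The strongest defence is that the headed SAE definition governs. It is mandatory in tone, has no grade or causality filter, and comes with a requirement to record every SAE. The disputed sentence is only a remark under a causality table, and the sentence before it takes SAE status as given. On that reading the remark merely sorts drug reactions into serious and non-serious. Severity may also be a loose rendering of seriousness, since the document has other awkward wording, such as the name given to the sample size module in section 3.3.

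Much of this stands. The remark does not say that unrelated events cannot be SAEs, and the recording requirement remains in force. Misclassification is therefore a risk if staff follow the remark, not a certainty. The grade 2 example also assumes that severity means CTCAE grade, which the remark does not state.

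The defence does not remove the conflict. Even if severity means seriousness, the sentence still makes classification conditional on relatedness, which the definition does not. The defence also depends on the reader deciding which sentence prevails, and the protocol does not say.

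Stronger readings are tempting but not supported:

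- *The stated safety comparison is distorted.* The secondary endpoint is adverse events graded by CTCAE 5.0. These are recorded and graded for all events regardless of SAE status, and the protocol names no between-arm SAE endpoint.
- *The efficacy data are affected, because an SAE is a listed ground for investigator withdrawal (Part III, section 3.1).* This needs a mislabelled event, then a changed withdrawal decision, then missing mucositis data. Nothing in the document establishes that chain, and the label does not alter membership of the Full Analysis Set.
- *Hospitalisation will be the commonest kind of SAE, so the loss will be large.* The document gives no figure for this.

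**Conclusion.** The inconsistency is real and is in current protocol text. The definition and the final causality remark use different criteria and different conditions, and the remarks disagree with themselves on whether SAE status comes before or after causality. It is a wrong instruction, not a missing detail.

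Its reach is limited to SAE recording and SAE counts by arm. Its size cannot be derived from the document: there are no expected SAE numbers, no severity threshold, and no indication of which sentence sites would follow. The direction is also unknown. A reader might infer that SAEs will be under-counted, or under-counted mainly in the Sapylin arm because the causality table requires a fit with the known reaction profile before an event is called related. The document does not support either inference, because unrelated events are not expressly excluded and a severity test can add SAEs as well as lose them.

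The conclusion assumes that some staff will apply the remark as written. It has no bearing on the primary endpoint, the sample size or the CTCAE-graded adverse event endpoint.

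**What to change.** Reconcile the two places in section 6:

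1. Delete the clause in the causality remarks that makes SAE status depend on severity.
2. State in its place that SAE status follows the listed criteria in the SAE definition for every adverse event, whatever its CTCAE grade and whatever the causality judgement.
3. Record CTCAE grade and causality on the case report form as fields separate from SAE status.

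The list's last item, Other, is undefined, so a short description of what it covers would help the list work as the sole criterion.

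The cost is a one-sentence amendment and a check that the report forms match. Slightly more SAE forms may be filed. If SAEs have already been classified, those records should be checked against the outcome list so that early and late patients are counted the same way.
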